## Introduction

Cyclic vomiting syndrome (CVS) is a disorder of gut-brain interaction (DGBI) characterized by episodes of intense vomiting that are often triggered by stress. CVS affects 2% of the population and negatively impacts patients. Although gastrointestinal symptoms are prominent, most patients have comorbid anxiety, depression, and high degrees of psychological distress that adversely affect health-related quality of life (HRQoL) and patient outcomes. Further, stress is known to trigger episodes of CVS in ~ 80% of patients.(9) The exact mechanism of how stress influences the gut-brain axis in CVS is not clear. It is hypothesized that CVS is a disorder of allostatic dysregulation whereby multiple biopsychosocial factors including chronic stress, sleep deprivation, mood disorders and early life adversity can disrupt normal allostatic regulation and result in CVS episodes. CVS is likely multifactorial with a combination of genetic, environmental and neurohormonal factors that result in symptoms.

Nonetheless, it is crucial to address underlying stress and other psychological comorbidities that can drive symptoms and negatively impact influence overall HRQoL of these patients irrespective of typical measures of disease severity in CVS.(8) Recent guidelines recommend a biopsychosocial model of care incorporating techniques like meditation to mitigate stress and improve outcomes in CVS, but there are limited data to support this recommendation.

One such approach is Heartfulness meditation (HFM), which includes progressive relaxation with a concentrated focus on the heart to increase awareness of the present moment, reduce stress, and promote relaxation. HFM is a secular, guided meditation technique that is safe and offered free-of-charge. HFM has been shown to reduce perceived stress, and anxiety and improve well-being in normal subjects. Our overall objective was to determine the efficacy of HFM deliver via an app. The specific aims of our study are listed below.

**Specific Aim 1a:** Conduct a prospective study to elucidate the *acute effects* of HFN meditation on the ECSS in CVS. We will measure circulating endocannabinoids and related lipids immediately before and after HFN meditation.

**1b**: Correlate indices of ECSS with state anxiety and mood pre-and post-HFN meditation. We will measure state anxiety and mood with validated tools including the State Trait Anxiety Inventory (STAI) and Profile of Mood States (POMS) which evaluates tension, depression, anger, vigor, fatigue, and confusion.

*Hypothesis*: HFN meditation will acutely increase circulating endocannabinoids which will be correlated with a reduction in state anxiety and improvement in mood.

**Specific Aim 2:** Determine the *long-term effects* of a 6-week HFN meditation program on ECSS and correlate with psychological outcomes including psychological distress, STAI scores, sleep quality, and HRQoL. We will measure these outcomes with validated tools including the Brief Symptom Inventory (BSI), STAI, Pittsburgh Sleep Quality Index (PSQI), and PROMIS quality of life questionnaires.

*Hypothesis*: A regular HFN meditation practice over 6 weeks will further augment ECSS, and this will be result in an improvement in psychological outcomes such as psychological distress, sleep, mood and HRQoL.

## Study protocol

This study was approved by the Institutional Review Board at the Ohio State University and registered with clinicaltrials.gov (Registration number: NCT05961995). All participants signed an informed consent prior to this 6-week single-arm study.

#### Development of the Heartfulness meditation app and meditation protocol.

We developed a HIPAA complaint smartphone application (app) for delivering HFM that was self-paced and convenient for patients to use. The meditation app was developed in conjunction with the Heartfulness Institute, a non-profit global organization that offers HFM free-of-charge and has certified instructors. A standard script was used for the instructional video and recorded with the help of a certified experienced Heartfulness instructor. App users were encouraged to complete a half-hour meditation session three times weekly throughout the six-week intervention period. he app is HIPAA compliant, collecting no personal identifying information, and monitored compliance by recording the number of sessions completed.

#### Inclusion and exclusion criteria

Patients aged 18-80 years diagnosed with CVS based on Rome criteria were eligible to participate. Exclusion criteria included: (1) Major psychiatric illness such as schizophrenia, bipolar disease, and major depression or anxiety that was *not* controlled with medication or requiring inpatient care within the past year; (diagnosis was made by the patient's primary care provider or psychiatrist) (2) history of suicidal attempt/ideation in the past year; (3) cognitive impairment that precluded the ability to meditate; (4) inability to sit for at least 30 minutes; (5) severe cardiopulmonary diseases, malignancy, or renal failure on dialysis; (6) organic gastrointestinal diseases or systemic diseases including but not limited to inflammatory bowel disease and chronic liver diseases; (7) pregnancy at the time of enrolment; (8) BMI < 18 or >35; (9) current regular cannabis use defined as use  $\ge 4$  times a week; and (10) significant prior meditation experience that included mindfulness, heartfulness, music therapy, and other forms of meditative movement practices like yoga and qi gong (continuous meditation practice for  $\ge 3$  months within the previous year).

# Study outcomes

#### Primary outcomes

The primary outcomes were state and trait anxiety and mood states, measured using the State-Trait-Anxiety Inventory (STAI)(26) and Profile of Mood States (POMS) respectively.(27) The STAI has two 20-item subscales that measure the temporary emotional condition of "state anxiety" (STAI-S) and the long-standing personal characteristic of "trait anxiety" (STAI-T), respectively. The STAI-S evaluates amount of current feelings of apprehension, tension, nervousness, and worry. The POMS is a 35-item validated questionnaire that assesses mood across the 6 mood states of tension, depression, anger,

vigor, fatigue and confusion. These outcomes were measured immediately before and after a meditation session at baseline, at 3 weeks, and at the end of study (6 weeks).

### Secondary outcomes

Psychological distress was measured using the Brief Symptom Inventory (BSI)(28). Healthrelated quality of life (PROMIS)(29), sleep quality (Pittsburgh Sleep Quality Index)(30) and coping (COPE)(31) were also measured with validated tools. These outcomes were all measured at baseline, weeks 3 and 6. Perceived intervention effectiveness was assessed with a visual analog scale (VAS) (from 0 = "not effective at all" to 10 = "most effective imaginable") after intervention sessions at baseline and at end of study. All questionnaires were completed on REDCap, a secure online platform for conducting research.

# Endocannabinoid concentrations and related lipids

Blood was collected for measurement of circulating endocannabinoid concentrations before and immediately after meditation sessions at baseline and at week 6 (first and last mediation sessions during the study). Serum concentrations of endocannabinoids *N*arachidonylethanolamine (AEA) and 2-arachidonoylglycerol (2-AG) and related lipids *N*oleoylethanolamine (OEA) and palmitoylethanolamide (PEA) were quantified by isotope dilution following measurement using atmospheric pressure, chemical ionization liquid chromatography/mass spectrometry (LC-APCI-MS).

Subjects completed the first and last meditation sessions at the clinical translational unit. These sessions were scheduled between 8 AM and 1 PM given diurnal variation in endocannabinoid concentrations. The remainder of the session were completed at home by subjects. All study questionnaires were completed at the beginning of the study (baseline), week 6 and 12.

# **Statistical analysis**

Patient characteristics were summarized using means and standard deviations or medians and interquartile ranges for continuous variables, depending on the distribution of the data. Frequencies and relative frequencies were used to describe categorical patient characteristics. Changes in means for state and trait anxiety, mood states, health-related quality of life, daytime sleepiness, subscale scores and index scores of the BSI, and subscales scores of the COPE were examined over time (baseline, week 3, and week 6) using repeated measures ANOVA. Paired t-tests were used to compare means of state anxiety, total mood disturbance, visual analog scale scores, and levels of serum endocannabinoids and related lipids before and after HFM at baseline and before and after HFM at 6 weeks. Analyses were performed using SPSS version 28.0 (IBM SPSS, Armonk, NY). The level of significance for all analyses was  $\alpha$ =0.05.

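### The three-visit repeated measures ANOVA uses only participants seen at all three visits; a mixed model would keep the others' data, and the week-3 schedule must be reconciled

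*Combined protocol and SAP*

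**What the plan says.** Under Primary outcomes: "The primary outcomes were state and trait anxiety and mood states", with visits at baseline, week 3 and week 6. Secondary outcomes gives the same three visits for distress, quality of life, sleep quality and coping.

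Under Statistical analysis, state and trait anxiety, mood states, quality of life, daytime sleepiness, BSI scores and COPE subscales "were examined over time (baseline, week 3, and week 6) using repeated measures ANOVA". Before/after comparisons within the baseline session and within the week-6 session use paired t-tests. The effectiveness VAS appears only under those t-tests, and PSQI sleep quality is not named in the ANOVA list. On software: "Analyses were performed using SPSS version 28.0". The SPSS procedure is not named.

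The section on endocannabinoid concentrations places the first and last sessions at the clinical unit and adds: "The remainder of the session were completed at home by subjects". The same section puts all questionnaires at baseline, week 6 and week 12, with no week 3.

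The available text defines no analysis population, no rule for withdrawals or missed questionnaires, no imputation, no mixed model and no sensitivity analysis.

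**The concern.** A classical repeated measures ANOVA needs a value at every level of the time factor. In its usual SPSS form, a participant with one missing visit is dropped from that outcome's test. Deletion is made outcome by outcome, so the analysed group can also differ between outcomes.

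Two kinds of usable data are thrown away: the baseline and week-6 scores of someone who misses only week 3, and the baseline and week-3 scores of someone who stops after week 3. The first loss is a pure waste of precision even when missingness is harmless. The second can also bias the result: if those who worsen by week 3 are the ones who leave, the means of those who remain improve without any true change. In a single-arm study no control group would show this.

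Missed questionnaires are plausible. Practice was self-paced and mostly at home, with only an encouragement to keep to it: "App users were encouraged to complete a half-hour meditation session three times weekly throughout the six-week intervention period".

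**Working it through.** The documents give no sample size, SD, correlation or dropout rate, so there is no plan figure to reproduce. Every rate below is an assumption.

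**1. Method property.** A standard repeated measures ANOVA routine (statsmodels AnovaRM) stopped with an unbalanced-data error when one visit of one participant was removed. The method cannot use an incomplete row.

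**2. Data loss.** Let m3 and m6 be the shares missing weeks 3 and 6, independently.

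- Kept by the ANOVA: (1 − m3)(1 − m6). Having a baseline/week-6 pair: 1 − m6.
- m3 = 20%, m6 = 10%: 0.8 × 0.9 = 72% kept; 90% have the pair. The difference is 90 − 72 = 18% of participants.
- m3 = m6 = 10%: 81% kept against 90%. m3 = m6 = 20%: 64% against 80%.

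**3. Direction of bias, by formula.** Write Y0, Y3, Y6 for the three scores, with common SD σ, equal correlation r and no true change.

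- Selection on worsening (Y3 − Y0): Cov(Y6 − Y0, Y3 − Y0) = σ²(1 − r) and Var(Y3 − Y0) = 2σ²(1 − r). The slope is 1/2, so the false week-6 change is half the false week-3 change.
- Selection on the week-3 level alone: Cov(Y6 − Y0, Y3) = σ²(r − r) = 0, so the week-6 change is unbiased.
- Random dropout: no bias in either.

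**4. Size, by simulation.** n = 30, SD 10, r = 0.6, no true change, dropout after week 3 with log-odds 1 to 2 per SD of worsening by week 3. That multiplies the odds by e¹ = 2.7 to e² = 7.4 per SD. Nominal level 5%.

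| Dropout | Overall time test rejects | Baseline-to-week-6 contrast rejects |
|---|---|---|
| 20% | about 11–20% | about 8–9% |
| 30% | about 15–33% | about 8–14% |

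Runs with other random seeds move these by up to about three percentage points. Across both rows the false change is −1.6 to −3.3 points at week 3 and −0.8 to −1.7 at week 6, as the one-half rule predicts. With dropout unrelated to outcome, the ANOVA rejected in 4.6 to 5.7%.

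**5. Milder assumptions.** With odds doubling per SD and 20% dropout, the overall test rejects in about 9% and the week-6 contrast in about 6%. In large samples with odds doubling, 10 to 30% dropout and r of 0.5 or 0.7, the false week-6 improvement is 0.02 to 0.10 SD (0.2 to 1.0 points at SD 10).

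**6. What a likelihood analysis of all visits does.** When dropout depends on observed worsening, its week-6 bias is within 0.05 points. When week-6 scores are missing because of week-6 worsening itself (n = 30, 20% missing), complete cases are biased by −1.6 to −2.3 points and the likelihood estimate still by −1.15 to −1.7. Since 1.15/1.6 = 0.72 and 1.7/2.3 = 0.74, nearly three quarters remains.

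**The case against.** Several objections are fair.

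- **The plan does not say listwise deletion.** True: it is a property of the named method, and SPSS can fit a mixed model. But the plan names the ANOVA and nothing in it points elsewhere. This does not remove the concern.
- **The large error rates belong to the overall time test.** A reader might take the 11 to 33% as the error rate of the 6-week result. It is not. It is driven mainly by week 3, the visit on which the simulated dropouts are selected. The week-6 contrast rejects in about 8 to 14%.
- **The dropout mechanism was assumed.** A reader might infer from the Introduction, which says "stress is known to trigger episodes of CVS in ~ 80% of patients", that distressed patients are the ones who leave. That sentence is about what triggers episodes, not about withdrawal. People who feel better might equally stop. Questionnaires were completed online, so practising at home or stopping the app need not prevent completion.
- **A mixed model is no cure for every mechanism.** This stands in full: if someone misses a visit because of how they are at that visit, most of the bias remains (step 6). The error rate of the recommended model at this size was also not simulated.
- **Week 3 may not exist.** If questionnaires followed the schedule in the endocannabinoid section, there are no week-3 data and the three-visit ANOVA cannot be run as written. The conflict must be settled first.

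**Conclusion.** The concern holds as a weakness of the chosen method. The primary outcomes and most questionnaire secondary outcomes go to an analysis restricted to participants with all three visits, and no stated rule overrides this. The loss of usable data is certain once anyone misses a visit; the 72% against 90% is an illustration under assumed rates.

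The bias is of unknown size and direction. It is nil under random dropout, and nil for the week-6 change if dropout follows only the week-3 level with equal correlations. Under the assumed strong selection on worsening it is about 0.8 to 1.7 points at week 6, and smaller under milder selection.

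Two wider readings are not supported. The documents do not show that a reported 6-week improvement would be an artefact of dropout. Nor does the restriction reach every questionnaire outcome: the VAS is analysed by paired t-test only, PSQI sleep quality is not named in the ANOVA list, and the paired t-tests are untouched by a missed week 3. The change is worth making because it is cheap and uses more of the data under a weaker assumption.

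**What to change.** In Statistical analysis:

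1. Replace the repeated measures ANOVA with a linear mixed model for repeated measures: visit as a categorical fixed effect, unstructured covariance, restricted maximum likelihood with a small-sample degrees-of-freedom correction (SPSS MIXED). Include all observed visits of every participant with a baseline score.
2. Name the baseline-to-week-6 contrast explicitly, so that the 6-week conclusion does not rest on the overall time test.
3. Report the number observed at each visit for each outcome, and baseline scores of completers and non-completers side by side.
4. Keep the complete-case ANOVA as a secondary analysis.
5. Add a simple missing-not-at-random sensitivity analysis, for example a range of delta shifts applied to missing week-6 scores. The complete-case ANOVA cannot serve this purpose.
6. Reconcile the questionnaire schedule in Primary and Secondary outcomes (baseline, weeks 3 and 6) with that in the endocannabinoid section (baseline, weeks 6 and 12), and make the visits in the model match.

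The cost is revised wording and slightly more analysis in software already named. The text is in the past tense, but none of these steps needs new data collection. The price in assumptions is missing at random given the observed scores. This is weaker than what the complete-row ANOVA needs, but still untestable, hence item 5.

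### The analysis section states no between-visit test of endocannabinoid change, which the Aim 2 hypothesis needs, and also omits the correlations promised in Aims 1b and 2

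*Combined protocol and SAP*

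**What the plan says.** The Introduction sets out the aims. Aim 2 is to determine the long-term effects "of a 6-week HFN meditation program on ECSS and correlate with psychological outcomes", and its hypothesis reads "A regular HFN meditation practice over 6 weeks will further augment ECSS". Aim 1b is to "Correlate indices of ECSS with state anxiety and mood pre-and post-HFN meditation", and the hypothesis under it is that "HFN meditation will acutely increase circulating endocannabinoids which will be correlated with a reduction in state anxiety and improvement in mood".

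The section on endocannabinoid concentrations has blood drawn before and just after the session at baseline and at week 6. Each participant therefore has four values of each of four lipids (AEA, 2-AG, OEA, PEA).

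The Statistical analysis section names descriptive summaries, a repeated measures ANOVA over baseline, week 3 and week 6, and paired t-tests. The ANOVA list covers anxiety, mood, quality of life, daytime sleepiness, BSI and COPE, but no lipid. The lipids appear only in the paired t-test sentence, as "levels of serum endocannabinoids and related lipids before and after HFM at baseline and before and after HFM at 6 weeks". The section names no correlation, regression or other measure of association.

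**The concern.** A hypothesis that six weeks of practice adds to the endocannabinoid response is a statement about change between visits. The stated lipid tests look only inside a visit: one asks whether levels move during the first session, the other whether they move during the last. Neither asks whether week 6 differs from baseline.

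If the plan is followed, the endocannabinoid part of Aim 2 ends with no test and no interval. A reader will then be drawn to compare the two within-session p-values, which is not a test of a difference. The missing correlations are a lesser gap of the same kind: two aims promise an association, and the analysis section does not say how it will be estimated, from which scores, or at which session.

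**Working it through.** The plan gives no figure to reproduce, so the first step is a comparison of the text. The later steps are illustrations on assumed values.

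**Step 1. Aims against stated analyses.**

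| Promised in the Introduction | Stated in Statistical analysis |
|---|---|
| Acute lipid change (Aim 1a) | Paired t-test within each visit: 2 per lipid, 8 in all |
| Further rise over 6 weeks (Aim 2) | No between-visit lipid contrast |
| Correlation with state anxiety and mood (Aim 1b) | None |
| Correlation with distress, STAI, sleep, quality of life (Aim 2) | None |

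Write the four values as pre0, post0, pre6, post6. Two contrasts could express the Aim 2 hypothesis: (a) pre6 − pre0, and (b) (post6 − pre6) − (post0 − pre0). The documents choose neither.

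**Step 2. Can the planned results supply contrast (a)?** The visit means give a point estimate, but the standard error needs the between-visit correlation r. Assume unit SD and n=30, so SE = √(2(1−r)/30), with 29 df. For a 0.5 SD rise:

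| r | SE | t | p |
|---|---|---|---|
| 0 | 0.258 | 1.94 | 0.06 |
| 0.4 | 0.200 | 2.50 | 0.018 |
| 0.8 | 0.115 | 4.33 | 0.0002 |

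The means are the same and the answers differ. The planned tests do not report r.

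**Step 3. Can they supply contrast (b)?** Assume a correlation of 0.8 between pre and post within a session. The SE of one within-session change is √(2(1−0.8)/30) = √(0.4/30) = 0.115. Acute changes of 0.25 and 0.5 SD then have planned p=0.039 and p=0.0002. Their difference, 0.25 SD, has SE = 0.115 × √(2(1−ρ)), where ρ is the correlation between the two within-session changes:

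| ρ | p for the difference | Power of (b) for a true 0.25 SD difference |
|---|---|---|
| 0 | 0.14 | 32% |
| 0.3 | 0.08 | 42% |
| 0.5 | 0.04 | 55% |
| 0.7 | 0.009 | 77% |

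Sample size matters too: at ρ=0, power is 22%, 32% or 49% for n=20, 30 or 50.

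**Step 4. What does comparing the two p-values do?** Suppose the true acute effect is identical at both visits. If ρ=0, the chance of significance at week 6 only is power × (1 − power): 0.5 × 0.5 = 25%, or 0.8 × 0.2 = 16%. Simulation (n=30, 40,000 trials) at power 0.5 gives 25%, 21%, 17% and 13% for ρ=0, 0.3, 0.5 and 0.7. At power 0.8 the figure falls from 16% to 9% over the same range.

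**Step 5. Price of the added lipid tests.** With no true effects, n=30, correlation 0.8 within a session and 0.4 between visits, the simulated chance of at least one false lipid positive goes from 33% (8 tests) to 49% (16 tests) if the lipids are independent. It goes from 29% to 43% if they correlate 0.5.

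**Step 6. Number and precision of the correlations.** With one score per instrument, Aim 1b gives 4 lipids × 2 scores × 2 sessions = 16. Aim 2 gives 4 lipids × 5 scores = 20. The total is 36. By the Fisher z method, an observed r=0.3 has a 95% interval of −0.16 to 0.66 at n=20, −0.07 to 0.60 at n=30 and 0.02 to 0.53 at n=50.

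**The case against.** The strongest reply is that the paired t-test sentence is loosely drafted and might be meant to cover week 6 against baseline. It also lists the VAS, which Secondary outcomes says was taken "after intervention sessions at baseline and at end of study". The VAS therefore has no before-session value and can only be compared across visits. This shows that the sentence cannot be read literally for every variable. It does not supply a lipid contrast: the words attached to the lipids pair before with after inside each visit, and if a cross-visit comparison was intended, (a) and (b) are different quantities and the plan picks neither.

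A second reply is about weight. No endocannabinoid is listed among the primary or secondary outcomes, and the paired t-test is already named, so only the contrast is missing. This stands, and it limits the point to the mechanistic aims. Those are nevertheless the subject of Specific Aims 1 and 2.

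A third reply is that the illustrations depend on unknown correlations and that a single figure could pick the worst corner. This also stands, which is why ranges are shown.

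The choice of change scores for Aim 1b is likewise a judgement. Its wording would also allow correlating levels at each time, although the accompanying hypothesis speaks of a rise linked to a reduction.

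**Conclusion.** The point holds and should be fixed. The stated within-session tests do not address the between-visit hypothesis of Aim 2, and the planned output cannot be turned into a test of it. The absence of the promised correlations is real but secondary. The textual finding needs no assumption. Every figure is illustrative and rests on the assumed n, unit SD and correlations.

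A reader might infer more than the documents support:

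- **That Aim 2 is untestable.** It is not. All four blood samples are collected, and the gap is in the stated analysis only.
- **That the trial's main results are compromised.** STAI and POMS have both within-session and cross-visit analyses, and the primary outcomes are unaffected.
- **That comparing p-values misleads in a fixed 25% of trials, or that contrast (b) has only 32% power.** Both figures hold only if the two within-session changes are uncorrelated. Over ρ from 0 to 0.7 the ranges are 25% to 13% (16% to 9% at power 0.8) and 32% to 77%.
- **That filling the gap would show an effect of meditation.** The design is described as a "prior to this 6-week single-arm study" format, so any between-visit contrast measures change over time.

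**What to change.** For each lipid, add a paired estimate with 95% confidence interval and test of (a) pre-session week 6 minus pre-session baseline and (b) the week-6 within-session change minus the baseline within-session change. State which of the two represents the Aim 2 hypothesis.

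Add the promised correlations as exploratory estimates with 95% confidence intervals, using one named coefficient (for example Spearman):

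- **Aim 1b:** within-session lipid change with change in STAI-S and in POMS total mood disturbance, at each of the two sessions with blood sampling.
- **Aim 2:** pre-session week-6 minus baseline lipid change with change in one named summary score each for BSI, STAI-S, STAI-T, PSQI and PROMIS.

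The outcome sections give questionnaire visits at weeks 3 and 6, while the endocannabinoid section gives weeks 6 and 12. Both include baseline and week 6, so these change scores are defined under either schedule. Interpret all additions as change over time. The methods are mostly written in the past tense, so label the additions post hoc if the data have already been analysed.

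The work is small and uses samples and questionnaires already in the study. The statistical cost is 8 more lipid tests, with the rise in false positives shown above, and about 36 correlations. Acknowledge the multiplicity, and report the correlations as estimates and not as tests. Precision will probably be modest, so the intervals should carry the interpretation.

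### The plan tests the before/after session change separately at baseline and week 6, never tests whether it differs between visits, and does not say which session score enters the three-visit ANOVA

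*Combined protocol and SAP*

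**What the plan says.** The Primary outcomes section of the combined protocol and SAP states: "The primary outcomes were state and trait anxiety and mood states". On timing it says: "These outcomes were measured immediately before and after a meditation session at baseline, at 3 weeks, and at the end of study (6 weeks". Taken at face value, that is six scores per scale and participant (3 visits x 2).

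The Statistical analysis section uses them in two ways.

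- **Acute change:** "Paired t-tests were used to compare means of state anxiety, total mood disturbance, visual analog scale scores", and also of the serum lipids, "before and after HFM at baseline and before and after HFM at 6 weeks". Week 3 is not named.
- **Change over time:** means of state and trait anxiety, mood states and several secondary scales "were examined over time (baseline, week 3, and week 6) using repeated measures ANOVA". Time is the only factor stated. The text does not say which of a visit's two scores is used.

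Blood was drawn "before and immediately after meditation sessions at baseline and at week 6", so there is no week-3 lipid sample. The lipids appear in the paired t-tests but not in the ANOVA list. Under Aim 2 in the Introduction the hypothesis reads: "A regular HFN meditation practice over 6 weeks will further augment ECSS".

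The section on endocannabinoid concentrations places the first and last sessions at the clinical unit between 8 AM and 1 PM. Of the others it says: "The remainder of the session were completed at home by subjects". It also puts all questionnaires at baseline, week 6 and week 12, which conflicts with the week 3 and week 6 schedule given elsewhere.

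**The concern.** Two questions are left open.

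The first is what the ANOVA estimates. Pre-session scores across visits describe a lasting change. Post-session scores also carry any change in the immediate response to a session. These are primary outcomes, and an unstated choice can be made after the data are seen.

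The second is whether the acute response changes with practice. Two separate within-visit tests do not answer this, because a difference in significance is not a test of a difference. The omission matters most for the lipids, since they carry the only stated hypothesis that practice adds to the effect. Whether that hypothesis means a larger acute response or a higher resting level, no listed test addresses it.

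The week-3 session scores are also left out of the acute analysis. That is a smaller matter of efficiency.

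**Working it through.** The documents give no sample size, power, effect size or SD, so there is no planned figure to reproduce. The check sets collection against analysis and then illustrates the size with assumed inputs.

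**Step 1. Collection against analysis**

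| Outcome | Before/after scores | Acute t-tests | Three-visit ANOVA | Test comparing acute changes |
|---|---|---|---|---|
| State anxiety | baseline, wk 3, wk 6 | baseline, wk 6 | yes, score not specified | none |
| POMS | baseline, wk 3, wk 6 | baseline, wk 6 (total mood disturbance) | yes, score not specified | none |
| Trait anxiety | baseline, wk 3, wk 6 | not listed | yes, score not specified | none |
| Lipids | baseline, wk 6 | baseline, wk 6 | not listed | none |

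**Step 2. What each choice of score estimates**

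Write the mean pre-session score at visit v as L(v) and the mean post-session score as L(v) + A(v), where A(v) is the acute effect. The change from baseline to week 6 is then:

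- pre-session scores: L(6) - L(0)
- post-session scores: [L(6) - L(0)] + [A(6) - A(0)]
- average of the two: [L(6) - L(0)] + [A(6) - A(0)]/2

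These agree only if A(6) = A(0), which the plan never tests. This step needs no assumed number.

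**Step 3. What week 3 would add to the average acute effect**

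The standard error of the mean of k session changes with common correlation rho, relative to one session, is sqrt((1 + (k - 1)rho)/k).

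- k = 2: sqrt(1/2) = 0.71 at rho = 0; sqrt(1.5/2) = 0.87 at rho = 0.5
- k = 3: sqrt(1/3) = 0.58 at rho = 0; sqrt(2/3) = 0.82 at rho = 0.5

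The plan already uses two sessions, so the relevant ratio is three to two: 0.58/0.71 = 0.82 and 0.82/0.87 = 0.94. Week 3 cuts the standard error by about 18% (rho = 0) to 6% (rho = 0.5). At n = 30 and effect 0.5, power for the average goes from 0.96 to 0.996, or from 0.86 to 0.90.

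**Step 4. Separate tests against a direct test when nothing changes**

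Assumed: the same true acute effect at both visits, 0.5 SD of the before/after change; two-sided alpha 0.05 (the plan gives 0.05 but not the sidedness); 20,000 simulated trials per setting. Single-test power p comes from the noncentral t distribution. For independent tests the chance that exactly one is significant is 2p(1 - p).

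| n | p | 2p(1 - p) | Simulated, rho = 0 | Simulated, rho = 0.5 | Direct test, false positives |
|---|---|---|---|---|---|
| 20 | 0.565 | 0.49 | 0.496 | 0.335 | 0.050-0.051 |
| 30 | 0.754 | 0.37 | 0.369 | 0.259 | 0.051-0.053 |
| 40 | 0.869 | 0.23 | 0.227 | 0.168 | 0.052 |

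A split result therefore appears in about 17-50% of trials with no true change. The direct test, which compares the week-6 change with the baseline change within participants, is wrong in about 5%. The range depends on power: at n = 60 and effect 0.5 the split rate is 5-6%, and at n = 40 and effect 0.8 it is 0.3%.

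**Step 5. What the direct test can detect**

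At n = 30, if the acute effect doubled from 0.5 to 1.0, the direct test would have power 0.47 (rho = 0) to 0.75 (rho = 0.5). It is valid, but in a small study a null result would not show that the effect is constant.

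**The case against.** Several points on the other side stand.

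- **Week-3 pairs may not exist.** Their collection before and after a session rests on the Primary outcomes section alone. The Secondary outcomes and Statistical analysis sections confirm a week-3 assessment but not its pairing with a session, and the endocannabinoid section has no week-3 questionnaire. A reader might infer that collected primary data are being wasted. The documents do not settle that, and week 3 is in any case used in the ANOVA.
- **Using only the clinic sessions is defensible.** It matches the blood sampling, and Aim 1b correlates the lipids with state anxiety and mood around a session, which is possible only at those two visits. The plan does not give this reason.
- **Week 3 is not a clean control for the blood draw.** A reader might infer that it is, because no blood is taken. But that session would, it appears, be at home and has no stated time window, so setting and time of day differ too.
- **The gain from week 3 is small.** Setting three sessions against one gives a relative standard error of 0.58-0.82, which a reader might take as the benefit. The plan already has two sessions, so the gain is 6-18%.
- **No misuse is planned.** A reader might infer that the sponsor intends to compare significance at one visit with non-significance at the other. Nothing in the text says so; the split-result rate is the risk if the results are read that way.
- **No aim says the acute effect on anxiety or mood grows with practice.** For those scales a test of change is needed only if such a claim is made.

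None of this answers the unspecified ANOVA score or the missing week-6 against baseline test for the lipids.

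**Conclusion.** The concern holds in this form. The lasting effect on the primary outcomes is not uniquely defined, because the ANOVA could take pre- or post-session scores and these differ by any change in the acute effect. No stated test compares acute changes between visits, or the week-6 lipids with baseline, although Aim 2 predicts augmentation. These conclusions rest on the text alone.

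The sizes are illustrative. A split pattern with no true change occurs in about 17-50% of trials at n = 20-40, effect 0.5 and correlation 0-0.5, against about 5% for the direct test; the rate falls towards zero when power is high. Leaving week 3 out of the acute analysis costs a modest 6-18% in standard error, and only if those pairs were collected. The point should be addressed, since it can alter what is concluded and is cheap to correct.

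**What to change.** 1. Define the lasting effect on pre-session scores: week 3 and week 6, each against baseline.
2. For state anxiety and POMS total mood disturbance, fit one mixed model with phase (pre, post), visit and phase-by-visit. Use an unstructured covariance over the repeated scores (6 x 7/2 = 21 parameters) or random participant, participant-by-phase and participant-by-visit effects. A random intercept alone forces acute changes at different visits to be uncorrelated and can misstate the standard error.
3. Take the main acute effect, and its change with practice (week-6 change minus baseline change), from the two clinic sessions. Report the week-3 change and the three-session average as a sensitivity analysis, because setting and time of day differ.
4. For each lipid, test directly the pre-session level at week 6 against baseline and the difference between the two acute changes. State which of these the Aim 2 hypothesis means.
5. Reconcile the week 3 and week 6 schedule in the Primary outcomes, Secondary outcomes and Statistical analysis sections with the week 6 and week 12 statement in the endocannabinoid section. Use of the week-3 pairs depends on this.

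The cost is SAP wording, a few more model terms and slightly more analysis work, in the SPSS package already named. No new data are needed for items 1 to 4, provided the week-3 scores were collected as the Primary outcomes section says; the lipid tests and the two-clinic-session comparison do not depend on them.
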